10. PLANNED STATISTICAL METHODS

10.1 General Considerations

The statistical analyses described in this section will be performed as further outlined in the Statistical Analysis Plan (SAP), which will be finalized prior to database lock. The SAP will supersede the protocol if there are any differences between the two documents in the plans for data analysis and the differences will be noted in the SAP. The SAP will be included as an appendix in the clinical study report for this protocol. Statistical analyses will be performed using SAS 9.4 or higher.

Patients will be enrolled in this study after completing Study NS-065/NCNP-01-201 and will continue with the study dose (40 mg/kg/week or 80 mg/kg/week) they received in Study NS-065/NCNP-01-201. Results for this study will be summarized by study dose.

Statistical analyses will occur at the following times:

- Every 6 months. A report for the DSMB will be produced including all safety data available at the temporary data lock. A template report will be provided to the DSMB prior to the first report, and the report formats will be updated at the DSMB's requests as the data develop. The DSMB will review completeness of efficacy data, but will not review the efficacy data itself.
- At the conclusion of the study. A summary report will be generated on all baseline characteristics, safety assessments and efficacy assessments, addressing each of the primary, secondary and exploratory objectives of the study.

All statistical tests will be performed at a two-sided significance level of 0.05 with no corrections for multiple comparisons or multiple outcomes. Note however, that since this is an early phase extension study, with a focus on safety, the emphasis will not be on statistical tests (i.e., p-values).

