5.4. Blinding

Study NS-065/NCNP-01-202 is an open-label extension study and is not blinded.

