10.6.1 Primary Efficacy Objective

The primary efficacy outcome measure (TTSTAND) will be summarized by dose level over time using descriptive statistics. Actual values and change from the Pre-Infusion Visit (baseline from Study NS-065/NCNP-01-201) and change from Week 25 (baseline of the NS-065/NCNP-01-202 study) will be presented.

The TTSTAND times to perform the test will also be converted to velocities. (Note that a test result that is to be converted to velocity that the patient could not perform due to disease progression will have velocity set to zero only at the first visit where this occurs. After that visit, missing observations due to disease progression will be left as missing.). If needed, a data transformation or nonparametric approach will be performed for these assessments. Within patient changes and velocities (possibly transformed) will be tested using a one-sided paired t-test within dose level and within both dose groups combined.

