10.6.2.2 Analyses comparing NS-065/NCNP-01 patients to historical controls

A matched data set from the CINRG DNHS data will be created. The purpose of the matching is to create a group data set that corresponds in characteristics to the patients in this study. The CINRG DNHS data set includes patients from age 2 years to over 30 years old, and some have been followed for close to a decade. Therefore, it is important to create a comparator group which will allow valid group comparisons. No patient to patient matched analysis is proposed. The sole purpose of the matching is to create a historical control group which is comparable in its basic characteristics to the study patient group. The final CINRG DNHS data set is expected to have between 16 and 32 patients included with time intervals of evaluations between 6 and 15 months. TTSTAND, TTRW, TTCLIMB, NSAA, 6MWT, and QMT results will be compared between the NS-065/NCNP-01 patients and the CINRG DNHS patients possibly using mixed-effects linear

models. The TTSTAND, TTRW, and TTCLIMB times to perform the test will be converted to velocities. For a test that the patient could not perform, the velocity will be set to zero.

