10.7 Interim Analyses

Safety analyses are planned every 6 months as described above. Moreover, semi-annual reports to the DSMB will be descriptive and focus on safety.

In addition, interim analyses for safety are planned and interim analyses for efficacy may be conducted and further described in the Statistical Analysis Plan.

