10.8 Handling of Missing Data

Every effort will be made to collect all data. However, despite best efforts, missing or incomplete data may be reported. All missing or partial data will be presented in the patient data listing, as they are recorded on the eCRF.

Patients lost to follow-up or withdrawn will be included in statistical analyses up to the point of their last evaluation. Unless otherwise specified, no imputation of values for missing data will be performed. Of note, since patients with DMD are expected to decline over time, imputing efficacy parameters by last value carried forward mostly biases towards patients appearing stronger or faster than they are, since it carries forward potentially a better value than the value at the time of the missed observation. Therefore, for this study, we will summarize how much data are missing, but do not expect to need to impute any data to accomplish the analyses as described. Details of handling missing data will be described in the Statistical Analysis Plan.

Missed assessments which occurred as a result of the COVID-19 pandemic will be entered on the COVID-19 Protocol Deviation Log by site personnel. It is anticipated that some or all assessments and laboratory tests required by the protocol schedule of events may be missed during the pandemic. Some of the missed assessments may be able to be collected at the next home or onsite visit. The missing data will be summarized in the Statistical Analysis Plan.

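### The SAP need be final only before database lock, so in this open-label study the DNHS control set, model and deciding contrast for TTSTAND may be settled after outcomes could be known

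*Combined protocol and SAP*

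**What the plan says.** - **SAP timing (10.1).** The analyses are to follow an SAP, "which will be finalized prior to database lock. The SAP will supersede the protocol if there are any differences between the two documents". No earlier milestone is given. Differences from the protocol are to be noted in the SAP, and it is to be appended to the clinical study report.
- **Blinding (5.4).** "Study NS-065/NCNP-01-202 is an open-label extension study and is not blinded".
- **Interims (10.7 and synopsis).** Beyond safety reporting, "interim analyses for efficacy may be conducted and further described in the Statistical Analysis Plan". Section 10.1 lists only six-monthly safety reports and an end-of-study analysis.
- **Primary objective 2 (2.1).** TTSTAND in treated boys against matched historical controls.
- **Control source (1.2).** DNHS holds more than 400 boys and men followed for up to a decade, with timed function tests at annual visits.
- **Control set (10.6.2.2).** It is still to be created, comparable in unspecified basic characteristics. "The final CINRG DNHS data set is expected to have between 16 and 32 patients included", with evaluation intervals of 6 to 15 months. A mixed-effects linear model is named only as a possibility.

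**The concern.** Database lock protects an analysis plan when treatment codes stay hidden until then. Nothing is hidden here. TTSTAND is scheduled at 16 visits from Week 37 to Week 217, and the comparator outcomes sit in an existing database. Only the DSMB is kept from efficacy results (10.1). No section restricts the sponsor, the statistician or whoever selects the controls.

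There is no concurrent control, so the DNHS comparison is the only analysis that can address primary objective 2. If its controls and model may be chosen with outcomes in view, a reader cannot tell how much of an apparent benefit comes from the drug and how much from the choice.

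**Working it through.** The plan has no power or sample-size figure to reproduce: Section 10.2 says the 16 or so patients were not chosen on statistical grounds. The check is first textual, then illustrative.

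**1. What is fixed and what is open for the DNHS comparison**

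| Element | Status |
|---|---|
| Treated population | Fixed: FAS (10.3, 10.6) |
| Control source | Fixed: CINRG DNHS (10.6, 10.6.2.2) |
| Scale | Fixed: velocity for timed tests. 10.6.2.2 scores an inability as zero; 10.6.1 does so for TTSTAND only at the first such visit |
| Type of comparison | Fixed: group level, not pair matched (10.6.2.2) |
| Test level | Fixed: two-sided 0.05, no multiplicity correction (10.1) |
| Control set size | Expected range only, 16 to 32 |
| Matching variables, index visit, selection algorithm | Open |
| Model and covariates | Open |
| Deciding contrast (baseline, time point, dose pooling) | Open: two baselines, 16 visits, optional pooling |

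The open rows are the ones that determine the estimate, and 10.1 lets them stay open until lock.

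**2. Effect of choosing the control set on the error rate**

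Assumptions not in the documents: an eligible pool of M = 40 to 100 boys, K candidate control sets drawn at random from it, normal outcomes, no drug effect, 16 treated boys, and the most favourable set kept. A favourable result is t above its 97.5% point (nominal 2.5%).

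Simulation, 6,000 runs per pool size, with set size varying from 16 to 32:

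| K | M = 40 | M = 60 | M = 100 |
|---|---|---|---|
| 1 | 2.6% | 2.6% | 2.6% |
| 5 | 6.0% | 7.1% | 7.6% |
| 10 | 8.5% | 9.9% | 11.2% |

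Fixing the set size widens the range. Sets of 32 from a pool of 40 with K = 5 give about 5%. Sets of 16 from a pool of 80 with K = 10 give about 12%. Hence roughly 5% to 12%.

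The figures stay well below those for independent analyses because the sets overlap and share the same treated boys. For reference, the two-sided chance of at least one p < 0.05 in K independent analyses is 1 − 0.95^K: 22.6% for K = 5 and 40.1% for K = 10. The overlapping sets above give 11.8% to 15.4% and 16.2% to 22.9% on the same two-sided count.

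**3. Effect on the estimate**

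Given the pool, the mean of a random set of n has standard deviation √[(1/n)(1 − n/M)], in units of the between-boy SD. Multiplying by the expected maximum of K standard normals (1.163 for K = 5, 1.539 for K = 10) gives the approximate spurious shift:

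- Smallest case (n = 32, M = 40, K = 5): √(0.03125 × 0.20) = 0.079; × 1.163 = 0.09 SD.
- Largest case (n = 16, M = 100, K = 10): √(0.0625 × 0.84) = 0.229; × 1.539 = 0.35 SD.

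**4. With the choices fixed in advance**

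One control set and one model restore the nominal level (simulated two-sided error 5.0% to 5.3%). This assumes comparable groups; it does nothing about confounding.

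**The case against.** The strongest reply is that this is an early-phase extension with a safety focus, that 10.1 plays down p-values, and that differences from the protocol must be noted in an SAP appended to the study report. Much of this stands and lowers the severity. It does not remove the point. Selection moves the estimate as well as the p-value, and where the protocol is silent there is no difference to note.

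The simulation can also be challenged. The pool size and K are assumed, and controls would be chosen by a matching rule rather than by random draws with the best kept. That is fair: the figures illustrate the scope left open and do not predict this study. Choice of model, visit or baseline is not included and would add to them.

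Four stronger readings are tempting but not supported:

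- **That the choices were made with results in view.** The text supplied contains no separate SAP, so its date cannot be checked, and an SAP finalised early would comply with 10.1. No section says who had access to TTSTAND or DNHS follow-up.
- **That even the transformation for the DNHS comparison is open.** The clause "If needed, a data transformation or nonparametric approach will be performed for these assessments" belongs to the within-patient tests in 10.6.1 and 10.6.2.1. Section 10.6.2.2 has no such clause.
- **That the SAP is meant to be written with efficacy data open**, because 10.8 says "The missing data will be summarized in the Statistical Analysis Plan". That sentence closes a paragraph on assessments missed through COVID-19. Counts of missed assessments are not TTSTAND results.
- **That interim looks inflate the error to 8.2% to 14.2%** (two to five unadjusted looks at 0.05). This applies only if success could be claimed at a look. The plan states neither such a claim nor a number of looks.

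Section 10.7 can also be read as expecting SAP text before an efficacy interim, but it does not require it. Its difference from 10.1 is a gap between scheduled and optional analyses more than a contradiction.

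**Conclusion.** The point holds as a weakness in a stated rule. Section 10.1 permits the undecided parts of the only comparison that addresses primary objective 2 to be settled after outcomes on both sides could be known. The documents show the permission, not its use.

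Under the assumptions in the working, choosing among 5 to 10 control sets takes a nominal 2.5% favourable error to roughly 5% to 12% and shifts the estimate by about 0.09 to 0.35 SD. That DNHS outcomes could be known to those building the control set is an inference from Section 1.2, not a statement in the plan.

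Sensitivity analyses over alternative control sets and post hoc labelling would help a reader judge fragility, but would not make the choice prespecified. Given the safety focus and the low weight on p-values, this is something the sponsor should fix rather than a fatal defect.

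**What to change.** 1. In 10.1, replace the database-lock deadline for the external comparison. Require the DNHS eligibility rules, matching variables, index visit, model and deciding contrast to be fixed in a signed, dated SAP before any further efficacy output is produced and before treated and DNHS outcomes are linked. An earlier date alone is not enough; the SAP must contain these items.
2. Select the control set from a DNHS extract that holds baseline data only. Because the database already exists, nobody can guarantee that its follow-up has never been seen; the extract and the linkage date are the workable safeguards.
3. List in the clinical study report every efficacy output seen by the SAP date, and label later changes post hoc.
4. Make 10.1 and 10.7 agree on whether efficacy interims take place.

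Cost: SAP work moves earlier, a baseline-only extract is needed, and there is less freedom to adapt the analysis later. No patients, visits or procedures are added.

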10.2 Determination of Sample Size

Approximately 16 patients from Study NS-065/NCNP-01-201 will enter this study. Because this is an open-label extension study conducted in patients who complete Study NS-065/NCNP-01-201, the sample size is not based on any statistical considerations.

10.3 Analysis Populations

All analyses will be based on the actual treatment each patient received. Two populations will be defined for data analysis: the Safety Population and the Full Analysis Set.

Safety Population

All patients who receive at least one dose of NS-065/NCNP-01 Injection 250 mg in both the dose-finding (NS-065/NCNP-01-201) and extension study (NS-065/NCNP-01-202) will be included in the Safety Population. The Safety Population is the primary analysis population for safety assessments.

Full Analysis Set (FAS)

All patients who receive at least one dose of NS-065/NCNP-01 Injection 250 mg in both the dose-finding (NS-065/NCNP-01-201) and extension study (NS-065/NCNP-01-202) will be included in the FAS. The FAS is the primary analysis population for clinical efficacy and exploratory PD assessments.

10.4 Demographics and Baseline Characteristics

Summaries of patient demographics (age, race, ethnicity and dominant hand), baseline safety characteristics (anthropometrics, vital signs, physical examination, hematology, chemistry, BNP, urinalysis, ECG and antibodies), and baseline efficacy parameters will be done by dose level. Note that two sets of baseline values will be summarized, Screening Visit (from Dose-finding Study NS-065/NCNP-01-201) and Week 25 (from Extension Study NS-065/NCNP-01-202).

Any differences in distribution of baseline characteristics will be noted, although with such a small study, it is to be expected that some differences will emerge.

10.5 Safety Assessments

Safety analyses will be performed using the safety population and will address one of two co-primary objectives of the study. All safety assessments will be based on actual treatments received by participants.

10.5.1 Anthropometrics, Vital Signs, Laboratory Assessments, and ECG

Anthropometrics, vital signs, hematology, chemistry, BNP, urinalysis, and ECG results will be summarized by dose level over time using descriptive statistics for continuous outcomes. Actual values and change from Screening Visit (hematology, chemistry and urinalysis) or Day 1 (anthropometrics, vital signs and ECG) from Study NS-065/NCNP-01-201 and change from Week 25 (baseline of the NS-065/NCNP-01-202 study) will be presented. Further, all lab abnormalities will be listed.

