1.3.4. Toxicology

Repeated administration of NS-065/NCNP-01 via the clinically relevant route of administration (weekly IV injections) in both mice and monkeys resulted in decreases in red blood cell parameters, increased values for cytokines and histopathological effects in the kidney, testes and/or urinary bladder. The kidney is the primary target organ in both mice and monkeys, as shown by increased values in clinical chemistry parameters indicative of renal effects (1000 mg/kg/dose in 13- and 26-week mouse studies or 600 mg/kg/dose in a 12-week monkey study) and by histopathological findings of effects in renal tubules (≥ 240 mg/kg/dose in 13- and 26-week mouse studies, ≥ 200 mg/kg/dose in a 12-week monkey study or 360 mg/kg/dose in a 39-week monkey study) occasionally accompanied by increased kidney weight at necropsy. This observation is consistent with the PK data that show high tissue distribution to the kidney and excretion via the urine. An additional histopathological finding in a 26-week mouse study was the presence of cytoplasmic eosinophilic material in the transitional epithelium of the urinary bladder at 60 mg/kg/dose and above. At high dose (1000 mg/kg/dose in 13- and 26-week mouse studies or 600 mg/kg/dose in a 12-week monkey study), reductions in red blood cell parameters were also seen. Higher doses in mice (≥ 240 mg/kg/dose in a 13-week mouse study or 1000 mg/kg/dose in a 26-week mouse study) showed increased values for interleukin-6 (IL-6), tumor necrosis factor-alpha (TNF- α) and/or monocyte chemoattractant protein-1 (MCP-1) and alterations in complement; these findings were considered to be due to irritation of the injection site. Data from 4- and 8-week recovery periods indicated a trend toward reversal of these effects in both species.

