1.3.5. Summary of Clinical Findings

1.3.5.1. Phase I

A Phase I investigator-initiated study of NS-065/NCNP-01 Injection was conducted in DMD patients (aged 5-18 years) to investigate the overall usefulness of NS-065/NCNP-01 Injection in the treatment of DMD, based on evaluations of safety, exploration of predictive markers of treatment response, and assessment of pharmacokinetics. A total of 10 DMD patients were enrolled and randomized. IV administration of NS-065/NCNP-01 Injection in doses of 1.25 mg/kg, 5 mg/kg and 20 mg/kg to DMD patients once weekly for 12 weeks was well tolerated, and no

dose-limiting toxicity was observed, although all patients had at least one AE. Moreover, neither serious adverse events (SAE) nor incidences of Common Terminology Criteria for Adverse Events (CTCAE) v4.03 Grade 3 (severe) or worse were reported.

Among the mild and moderate AEs, an increase in urine beta-N-acetyl-D-glucosaminidase (Grade 1) was found in all patients in both cohorts 1 and 2 [Cohort 1 (n=3) Cohort 2 (n=3)] and in all but one patient in Cohort 3 [Cohort 3 (n=4)].

Initially, testing appeared to reveal proteinuria in 8 of 10 patients. However, it was subsequently determined that there was a cross reaction between NS-065/NCNP-01 and the pyrogallol red dye-binding method which was used for urinary protein measurement resulting in a false positive result for protein in the 24-hour pooled urine samples. To evaluate the 24-hour pooled urine samples for protein, Coomassie brilliant blue method was used to re-measure urinary protein in the frozen urine samples and none of the retested samples showed urinary protein levels exceeding the normal range of the institution (i.e., 31.2 to 120 mg/day). Current studies utilize a urine protein Benzethonium Chloride method using reagents that do not cross react with NS-065/NCNP-01. NS-065/NCNP-01 exhibited no cross reactivity with the Benzethonium Chloride Method up to 500 mg/dL.

The 24-hour pooled urine samples did not show increased levels of albumin. Spot measurements of urinary albumin were positive in 7 patients (Grade 1).

Interleukin levels were increased (Grade 1) in the serum in 6 out of 10 patients (high IL-6 level in 4 subjects, high IL-1 β level in 1 subject, and high IL-2 level in 1 subject), and some level of anemia (Grade 1) was observed in 7 out of 10 patients.

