Pharmacokinetics and Pharmacodynamics	Pharmacokinetics and Pharmacodynamics													
PK (Blood) ¹¹														
Serum PD Biomarker												X		

Notes:

1. Week 25 of Study NS-065/NCNP-01-201 will also serve as Week 25 for first dose of Study NS-065/NCNP-01-202. End of study procedures of Study NS-065/NCNP-01-201 must be completed prior to dosing in Extension Study NS-065/NCNP-01-202
2. Perform vitals at pre-dose, at the end of infusion (+10 mins) and 1 hr (+/- 5 mins)
3. Hematology: RBC, Hb, Ht, Ret, MCV, MCH, MCHC, WBC, PLT, WBC Differential Fibrinogen, aPTT, PT-INR
4. Chemistry: Na, K, Cl, Ca, IP, BUN, Serum Creatinine, Cystatin C, AST, ALT, GGT, ALP, Haptoglobin, LDH/LDH isozyme, CK, Total bilirubin (Direct/Indirect), Total protein, Albumin, Albumin to globulin ratio, Total cholesterol, Triglyceride, Blood glucose, C-reactive protein
5. Urinalysis (Random Urine): Urine glucose, Urine blood, Urine urobilinogen, Urine specific gravity, Urine osmolarity, Urinary sediment (RBC, WBC, Cast), Urine protein (benzethonium chloride method), Albumin in urine, NAG in urine, α 1-microglobulin in urine, Urine Creatinine
6. Urine Cytology is collected along with pre-dose Urinalysis. Following Protocol Amendment 9.0 approval, the assessment should be performed at the next clinic visit, then every 6 months thereafter (i.e. Visits 133, 157, 181 and 193 or Visits 145, 169, 193, 205 and 217). Urine Cytology is collected at Visit 217 for all subjects.
7. 24hr pooled Urine in Study NS-065/NCNP-01-201 only: Urine protein (benzethonium chloride method) , Albumin in urine, NAG in urine, α 1-microglobulin in urine, Urine Cr, Urine Na, Urine K, Urine Cl, Urine IP, Uric acid in urine, β 2-microglobulin in urine and PK
8. Renal Ultrasound includes imaging of kidneys, bladder and ureters. Following Protocol Amendment 9.0 approval, the assessment should be performed at the next clinic visit, then every 6 months thereafter (i.e. Visits 133, 157, 181 and 193 or Visits 145, 169, 193, 205 and 217). Renal Ultrasound is collected at Visit 217 for all subjects.
9. Cytokine: IL-6, TNF- α , MCP-1 at pre-dose and 8hr (\pm 30min) after end of infusion
10. Function and Strength: Time to Stand (TTSTAND), Time to Climb (TTCLIMB), Time to run/walk 10 meters (TTRW), Six-minute walk Test (6MWT), North Start Ambulatory Assessment (NSAA), Quantitative Muscle Testing (QMT) and Ulnar Length
11. PK sampling timepoints: pre-dose, 1hr (+/- 5 mins) and 8hr (+/- 5 mins) after the end of the infusion

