9.5.2. Serious Adverse Event Reporting

All SAEs, including death due to any cause and whether or not deemed drug-related or expected, must be reported within the study EDC system (eCRF) within 24 hours (1 working day) of the Principal Investigator or the clinical site becoming aware of the occurrence.

The Investigators responsible for ongoing clinical studies with the investigational product will be notified by the CRO of all SAEs.

- **9.5.3 Adverse Events of Special Interest**

The following events are considered AEs of special interest based on the route of administration and toxicology profile for the study drug:

- Access device complication (for participants with indwelling access devices);
- Cystatin C $>1.5 \times$ ULN or $>1.5 \times$ baseline if baseline $>$ ULN;
- Urine protein-osmolality > 0.3 mg/L/mOsm/kg;
- Any confirmed instances of hematuria or other potentially clinically significant abnormalities on urinalysis.

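### Section 10.5.1 gives no dilution-indexed summary for the spot-urine kidney markers, although osmolality and creatinine are measured in the same panel, so the over-time renal tables carry avoidable noise

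*Combined protocol and SAP*

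**What the plan says.** **Planned summary.** Section 10.5.1 says: "Anthropometrics, vital signs, hematology, chemistry, BNP, urinalysis, and ECG results will be summarized by dose level over time using descriptive statistics for continuous outcomes". The scale is "Actual values and change from Screening Visit (hematology, chemistry and urinalysis") for Study 201, plus change from Week 25. The only other laboratory output it names is a listing: "Further, all lab abnormalities will be listed". It mentions no ratio to osmolality or creatinine.

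**What is measured.** Table 1, note 5, defines the spot panel, beginning "Urinalysis (Random Urine): Urine glucose, Urine blood, Urine urobilinogen, Urine specific gravity, Urine osmolarity". It goes on to protein, albumin, NAG, alpha-1-microglobulin and urine creatinine. Table 2 repeats the panel and calls the concentration measure osmolality. Note 7 of Table 1 confines the 24-hour pool to Study 201.

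**Where indexing is used.** Section 9.5.3 makes this an AESI: "Urine protein-osmolality > 0.3 mg/L/mOsm/kg". Serum cystatin C is another AESI in the same list.

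**Why the organ matters.** Section 1.3.4 says: "The kidney is the primary target organ in both mice and monkeys". In Phase I (Section 1.3.5.1), urinary NAG rose in all patients but one, at Grade 1.

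**Sampling.** Sections 8.1.3, 8.1.4 and 8.2.1 specify random urine. Sections 8.1.6 and 8.1.7 (Weeks 61, 85, 109 and every 12 weeks from 121 to 205) specify a pre-dose void and a first void within 5 hours after dosing. Section 10.5.1 does not say which void enters the tables.

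**The concern.** A marker's concentration in a spot sample depends on how much is excreted and on how dilute that void is. In a change table the two cannot be told apart. A boy who drank more before one visit appears to improve, and one who drank less appears to worsen.

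The protocol accepts this for protein when it defines an event, but does not carry the same scale into the laboratory tables. Albumin, NAG and alpha-1-microglobulin are not indexed anywhere in the document. These tables are where gradual change below an event threshold would be seen over up to 192 weeks, and with about 16 boys there is little averaging to absorb the extra noise.

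The post-dose void adds a further difference. It follows an intravenous infusion and may differ in dilution from a pre-dose void. If the two were pooled, the visits with paired voids would not be comparable with the earlier ones.

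**Working it through.** The plan states no figure to reproduce here, and Section 10.2 says the sample size has no statistical basis. The check has four steps.

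**1. Phase I NAG count (Section 1.3.5.1).** 3 of 3, 3 of 3 and 3 of 4 give 9 of 10.

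**2. What the AESI ratio means as a raw concentration.** Raw protein = 0.3 × osmolality. The osmolality values are assumed.

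| Osmolality (mOsm/kg) | Raw protein at the AESI ratio (mg/L) |
|---|---|
| 100 | 30 |
| 300 | 90 |
| 600 | 180 |
| 1200 | 360 |

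Over this range the same protein-to-osmolality ratio corresponds to raw values that differ 12-fold (360/30). A raw value of 100 mg/L exceeds the AESI ratio only below 100/0.3 = 333 mOsm/kg.

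**3. Noise from dilution alone.** Let s be the SD of log osmolality between voids, assumed to be 0.4 with range 0.3 to 0.5. Hold excretion constant and let concentration move in proportion to osmolality. The log change between two voids then has SD = √2 × s.

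- One boy, 95% range: exp(±1.96 × SD).
- Chance of an apparent rise of at least 2-fold: 1 − Φ(ln 2 / SD).
- Group geometric mean ratio, 95% interval: exp(±t × SD/√n), with t = 2.365 for n = 8 and 2.131 for n = 16.

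| s | SD of change | One boy, 95% range | P(rise ≥ 2-fold) | n = 8 | n = 16 |
|---|---|---|---|---|---|
| 0.3 | 0.424 | 0.44 to 2.3 | 5% | 0.70 to 1.43 | 0.80 to 1.25 |
| 0.4 | 0.566 | 0.33 to 3.0 | 11% | 0.62 to 1.60 | 0.74 to 1.35 |
| 0.5 | 0.707 | 0.25 to 4.0 | 16% | 0.55 to 1.81 | 0.69 to 1.46 |

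For s = 0.4 and n = 8: 2.365 × 0.566/√8 = 0.473, and exp(±0.473) = 0.62 to 1.60. Taking n = 8 assumes an even split of about 16 boys.

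**4. Ability to see a real rise.** Add a within-boy SD of log excretion, assumed to be 0.3. SD of change = √(2 × (0.3² + s²)). The test is a paired t-test, two-sided 0.05, for a true 1.5-fold rise. Power comes from the noncentral t distribution.

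| | Perfect indexing (s = 0) | Raw, s = 0.3 | Raw, s = 0.5 |
|---|---|---|---|
| n = 8 | 0.64 | 0.38 | 0.23 |
| n = 16 | 0.95 | 0.71 | 0.45 |

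The s = 0 column is a best case, because no ratio removes dilution completely. Power serves here only as a measure of precision, since Section 10.1 says the emphasis is not on tests.

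**The case against.** **The plan never says raw concentrations.** This stands. Actual values are contrasted with changes, and the absence of ratios is silence rather than refusal. Section 10.1 defers detail to a SAP that supersedes the protocol, and no separate SAP text is in the supplied document. The request is therefore to state the ratio, in either place.

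**Renal safety does not rest on these tables.** This also stands. Protein/osmolality and cystatin C are AESIs, and serum creatinine and BUN are measured. Section 9.11 requires urinalysis abnormalities to be confirmed by the following week's visit. Ultrasound and cytology were added, and all laboratory abnormalities are listed. A reader might infer that dilution can hide the drug's main toxicity, or that the primary safety objective is answered on the wrong scale. The documents do not support that. They do leave albumin, NAG and alpha-1-microglobulin unindexed, and protein indexed only as a threshold event.

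**Phase I does not prove dilution error.** Section 1.3.5.1 reports: "Spot measurements of urinary albumin were positive in 7 patients (Grade 1"), while pooled 24-hour urine showed no rise in albumin. A reader might take this as proof of dilution error. The section gives no cause, and sample timing or the positivity threshold would also fit. Nor does it say whether the NAG rise was in spot or pooled urine.

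**Random voids are not a different kind of sample.** Largely right. Section 8.1 requires activities in the listed order, and Sections 8.1.3 and 8.1.4 list random urine before dosing. Mainly the post-dose void differs, and nothing says it will be pooled.

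**The SD is assumed, and random dilution is noise rather than bias.** Correct. The calculation also compares one visit with one baseline, whereas the plan shows many visits.

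**Conclusion.** The point holds as a limited improvement to the analysis. For four spot-urine kidney markers the stated summary is less precise than one the collected data allow, and the protocol already uses the better scale for one of them.

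The effect is extra noise in the over-time tables. At an assumed log-osmolality SD of 0.3 to 0.5, dilution alone puts the 95% interval for a group ratio in 8 boys between 0.70 to 1.43 and 0.55 to 1.81. These figures are illustrative. They rest on that SD, on concentration moving in proportion to osmolality, and on an even split between doses. No systematic bias is shown. The kidney's status as primary target organ is a nonclinical finding, and the Phase I NAG and albumin findings were Grade 1.

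**What to change.** In Section 10.5.1 or the SAP:

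- Keep the actual values and changes. Beside them, tabulate protein, albumin, NAG and alpha-1-microglobulin as ratios to osmolality from the same void.
- Give the creatinine ratio as a supportive display only. Creatinine output may fall as muscle is lost, which would raise that ratio without any renal change.
- Present the ratios on the log scale, as geometric mean ratios to Week 25. Do the same against Study 201 Screening only where same-void osmolality exists. Note 5 of Table 1 supports it for Week 25. It is not confirmed for Screening, and the Study 201 24-hour panel in note 7 lists creatinine but not osmolality.
- Tabulate post-dose voids separately from pre-dose and random voids.
- Reconcile the void labels: Table 1 marks later urinalyses as random urine where Sections 8.1.6 and 8.1.7 specify paired pre- and post-dose voids. Also reconcile osmolarity (note 5) with osmolality (Table 2 and Section 9.5.3).

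The cost is some derived variables and tables, the same derivation for the Study 201 baselines, and loss of a ratio wherever osmolality is missing. No new sample or visit is needed, and the AESI definitions are untouched.
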